#### 2. SYNOPSIS

#### Name of Sponsor/Company:

Nabriva Therapeutics

#### Name of Investigational Product:

XENLETA® (lefamulin)

#### Name of Active Ingredient:

Lefamulin (BC-3781)

#### Title of Study:

A Phase 1, Open-Label, Randomized, Crossover Study to Assess the Safety and Pharmacokinetics Following Single Doses of Oral and Intravenous XENLETA® (Lefamulin) in Adult Patients with Cystic Fibrosis

Number of study centers: Approximately 6

#### Studied period (years):

Estimated date first patient enrolled: Jan 2022

Estimated date last patient completed: Mar 2023

#### Phase of development: 1

#### **Objectives:**

#### **Primary:**

• To evaluate the pharmacokinetics (PK) of a 600-mg immediate-release (IR) tablet and 150-mg intravenous (IV) formulations of lefamulin in adult patients with cystic fibrosis (CF)

#### **Secondary:**

• To evaluate the safety and tolerability of lefamulin when administered as single oral or IV doses in adult patients with CF

#### **Endpoints**:

#### **Primary:**

• Plasma PK parameters of lefamulin and its main metabolite BC-8041 following 150-mg IV infusion and 600-mg IR tablet in patients with CF.

#### **Secondary:**

Descriptive summaries of the following:

- Treatment-emergent adverse events (TEAEs)
- Laboratory assessments (chemistry and hematology)
- Vital signs measurements
- Electrocardiogram (ECG) parameters

#### Methodology:

This will be a single-cohort, open-label, randomized, 2-part, crossover study in patients receiving a single dose of lefamulin at 2 study periods 4 to 7 days apart. Lefamulin will be administered as a 600-mg IR tablet orally in the fasted state and a 150-mg IV infusion in 250 mL citrate buffered saline over 1 hour.

#### **Number of patients (planned):**

Approximately 12 patients are planned to be enrolled.

#### Diagnosis and main criteria for inclusion:

Key inclusion criteria are as follows:

- 1. Signed informed consent.
- 2. Adult patients,  $\geq 18$  years of age.
- 3. Genetic confirmation of CF diagnosis by a report from a genetic test, such as "F508 deletion detected."
- 4. Weight > 40 kgs.
- 5. Forced expiration volume (FEV)1 > 40% predicted, as measured during the most recent evaluation.
- 6. Mentally and physically able to participate in the study as determined by the Investigator, ie, clinically stable with no significant changes in health status within 28 days prior to, and including, Day 1.
- 7. Vital signs within the following ranges:
  - a. Tympanic temperature, < 38°C
  - b. Systolic blood pressure, 90 to 160 mmHg
  - c. Diastolic blood pressure, 50 to 90 mmHg
  - d. Heart rate < 100 beats per minute at rest
  - e. Respiration rate 12 to 20 breaths per minute
  - f. Oxygen saturation to be documented. No selection criteria; supplemental oxygen use is acceptable.
- 8. Negative beta-human chorionic gonadotropin (β-hCG) urine or serum pregnancy test for females of childbearing potential.
- 9. Willing to commit to acceptable methods of contraception as defined in the protocol.

#### Key exclusion criteria are as follows:

- 1. Known history of chronic liver or biliary disease, Gilbert's syndrome, or any of the following at Screening: aspartate aminotransferase (AST) or alanine aminotransferase (ALT) > 2 x upper limit of normal (ULN), total bilirubin > 1.5 x ULN.
- 2. Prolonged baseline corrected QT interval corrected according to Fridericia (QTcF) defined as > 440 ms (females) and > 430 ms (males).
- 3. Family history or presence of prolonged QTc syndrome, Torsades de Pointes, or known conduction defects (eg, bundle branch block, atrioventricular block).
- 4. Use of Orkambi® (lumacaftor/ivacaftor) within 28 days prior to Day 1.
- 5. Use of cytochrome P450 (CYP)3A substrates that prolong the QT interval within 24 hours prior to Day 1.

02 November 2021 6 Confidential

- 6. Use of strong and moderate CYP3A inducers or P-glycoprotein (P-gp) inducers within 28 days prior to Day 1.
- 7. Use of strong inhibitors of CYP3A4 within 24 hours prior to Day 1.
- 8. Serum potassium level below the normal reference range at Screening.
- 9. Known allergy to pleuromutilin class of antibiotic or any of the excipients of the lefamulin formulations.
- 10. Consumption of grapefruit, grapefruit juice, grapefruit products, pomelo, or Seville oranges within 24 hours before Day 1.
- 11. Use of vaporized nicotine or cannabidiol products, smoking (regularly or intermittently) more than 5 cigarettes (or equivalent) per day, or any use of tobacco other than in cigarettes or cigars within 28 days of Day 1.
- 12. Positive blood test for hepatitis C, human immunodeficiency virus (HIV), or hepatitis B antigen or core antibody (indicating active infection).
- 13. Positive test for drugs of abuse or alcohol at Screening or Day -1 that cannot be satisfactorily supported by medical history.
- 14. Use of an investigational product within the 30 days prior to Day 1 (3 months prior to Day 1 if the study drug was a new chemical entity).
- 15. Difficulty swallowing tablets.
- 16. Females who are pregnant or breastfeeding.
- 17. Does not have suitable venous access for multiple venipuncture or cannulation.
- 18. Any medical, psychological, cognitive, social, or legal conditions that, in the opinion of the Investigator, would interfere with the patient's ability to give an informed consent and/or participate fully in the study.
- 19. Any other reason, in the opinion of the Investigator, the patient is unsuitable to participate.

#### Investigational product, dosage, and mode of administration:

Study drug will be administered as follows to all patients after an overnight fast:

- IV Treatment Period: Lefamulin 150 mg in 250 mL citrate buffered saline IV infusion over 1 hour
- Oral Treatment Period: Lefamulin as a 600-mg IR tablet in the fasted state. The oral treatment will be swallowed whole with 6 to 8 ounces of water at least 1 hour before or 2 hours after a meal.

#### **Duration of treatment:**

Total duration of study participation for each patient will be approximately 10 to 13 days (from Screening to Follow-up).

#### Reference therapy, dosage, and mode of administration:

None

#### Criteria for evaluation:

#### **Pharmacokinetics:**

Blood samples will be taken for the measurement of PK parameters at the following time points in each part of the study:

• Pre-dose; 30 min, and 1, 1.5, 2, 4, 8, 12, and 24 hours post-dose.

02 November 2021 7 Confidential

Sputum samples will be collected first thing in the morning on Day 1 (pre-dose), and spontaneous sputum samples may be collected through 24 hours post-dosing as often as the patient can provide a sample. The exact time of the sputum collection will be documented for determination of PK parameters of lefamulin in sputum.

#### Safety:

Safety will be evaluated with the following assessments:

- Adverse events and concomitant medications will be monitored and recorded throughout the study.
- Clinical chemistry and hematology assessments will be performed at Screening, Day -1, and 24 hours post-dose; laboratory assessments will be conducted at Follow-up only if necessary.
- Vital signs will be measured at Screening, pre-dose on Day 1, at 0.5 hours, 2 hours, and 24 hours post-dose; vital signs will be measured at Follow-up only if necessary.
- Electrocardiograms will be performed at Screening, pre-dose on Day 1, and at 0.5 and 2 hours post-dose; ECGs will be performed at Follow-up only if necessary.
- Physical examination will be performed at Screening, Day -1 and at 24 hours post-dose; physical examinations will be performed at Follow-up only if necessary.
- Drugs of abuse and alcohol (breath test) Screening will be performed at Screening and Day -1.
- After the first dosing period of the study, a Follow-up Visit will take place 4 to 7 days after the final dose of lefamulin. This visit will also serve as the Screening Visit for the second dosing period. After the second dosing period, a Follow-up phone call will take place 4 to 7 days after the final dose of lefamulin to ensure the ongoing wellbeing of the patients. If a patient reports any TEAEs which represent a cause for concern (as determined by the Investigator) he/she will be required to attend the clinic for a Follow-up assessment. This will be considered an unscheduled visit.

Tolerability will be assessed by evaluation of the safety parameters and recorded adverse events.

#### Statistical methods:

#### **Pharmacokinetics:**

Presentation of PK data will be descriptive in nature and will be presented by treatment.

Appropriate non-compartmental techniques will be used to obtain estimates, including but not limited to, the following PK parameters (defined in the protocol) in plasma for lefamulin and the metabolite BC-8041 in plasma when possible and appropriate:

 $T_{lag}$  (oral dose only),  $T_{max}$ ,  $C_{max}$ ,  $AUC_{(0-last)}$ ,  $AUC_{(0-24h)}$ ,  $AUC_{(0-inf)}$ ,  $AUC_$ 

#### Safety:

Safety and tolerability will be assessed by monitoring adverse events (AEs) and concomitant medications, clinical chemistry and hematology laboratory assessments, vital signs, ECG results, and physical examination findings. A complete description of the safety analysis variables will be presented in the Statistical Analysis Plan.

**Table 1:** Schedule of Assessments

		IV Treatment Period and Oral Treatment Period											
		Day 1			Day 1 Post-dose								
Study Procedure	Screening a	Day -1b	pre- dose c	Day 1	0.5 h	1 h	1.5 h	2 h	4 h	8 h	12 h	24 h	Follow- up d
Assessment window	D -30 to -1		_	_	± 5 m	± 5 m	± 10 m	± 10 m	± 30 m	± 1 h	± 1 h	± 1 h	4 to 7 days
Informed consent	X												
Inclusion/exclusion criteria	X	X											
Demography	X												
Medical/medication history	X	X											
Physical examination e	X	X										X	
Height and weight	X												
Vital signs f	X		X		X			X				X	
12-lead ECG	X		X		Xg			$X^h$					
Blood for chemistry, hematology, virology	Xi	X										X	
Drugs and alcohol screen	X	X											
Pregnancy test (serum or urine) j	X	X											
Sputum collection k		X 4 X											
Study drug administration 				X									
Plasma for PK			X		X	X	X	X	X	X	X	X	
Adverse event monitoring	X	X	X	X	X	X	X	X	X	X	X	X	X
Medications			X	X	X	X	X	X	X	X	X	X	X
Discharge from CRU m												X	

#### Table 1: Footnotes for Schedule of Assessments (Continued)

Abbreviations: AE = adverse event CRU = clinical study unit; D = study day; ECG = electrocardiogram; h = hour(s); IV = intravenous; m = minute(s); PK = pharmacokinetics

- a. Informed consent must be obtained before study specific-procedures are performed. However, assessments performed as part of standard of care within the screening period may be used to determine eligibility.
- b. After completion of all Day -1 assessments, patients who remain eligible per entry criteria will be admitted to the CRU. Day -1 assessments do not have to be repeated if Screening occurred within 72 hours.
- c. Day 1 pre-dose testing and sample collection should be performed within 2 hours before dosing.
- d. A Follow-up phone call will take place 4 to 7 days after the final dose. For any AEs or other issues of concern, investigators, at their discretion, may ask patients to return to the study site for an in-person visit (this would be considered an unscheduled visit).
- e. Complete physical examinations will be performed at Screening and Day -1; a focused physical examination will be performed on Day 1 at 24 hours.
- f. Systolic blood pressure, diastolic blood pressure, body temperature, heart rate, respiratory rate, oxygen saturation
- g. IV Treatment Period only (following IV dosing)
- h. Oral Treatment Period only (following oral dosing)
- i. Includes viral serology at Screening
- j. Follicle stimulating hormone (FSH) level will be determined for women who are  $\geq 1$  year post-menopausal.
- k. Sputum should be collected first thing in the morning on Day 1 pre-dose, then collect as many sputum samples as possible.
- 1. IV Treatment Period: IV dose infused over 1 hour (± 2 minutes); Oral Treatment Period: the oral treatment will be swallowed whole with 6 to 8 ounces of water at least 1 hour before or 2 hours after a meal.
- m. Patient may be discharged from the CRU after completion of all 24-hour procedures and Investigator determination that no additional safety monitoring is required.

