## 8.5. Electrocardiograms

A 12-lead ECG will be performed at the time points specified in Table 1 after the patient has been resting in a supine position for 10 minutes. The Day 1 pre-dose ECG must be reviewed by the Investigator or their designee before dosing to ensure that there are no clinically significant findings that would prevent dosing. Additional ECGs may be performed at the discretion of the Investigator or when clinically indicated.

If a patient has an abnormal value ECG at Screening for either of the parts of the study, the ECG may be repeated twice. If after the second repeat measurement the value does not qualify the patient, he or she is not eligible for dosing. If the patient has prolongation of the QTc interval or any arrhythmia during the post-dose ECGs, no further lefamulin should be administered.

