#### **8.6.** Pharmacokinetics

## **8.6.1.** Plasma Sample Collection

Blood samples will be taken for the measurement of PK parameters at the following time points in each part of the study (Table 1):

• Pre-dose; 30 min, and 1, 1.5, 2, 4, 8, 12, and 24 hours post-dose.

For details on sample collection, preparation, and shipment, refer to the study-specific Laboratory Manual supplied by the Sponsor. It is recommended that the blood samples are taken by a venipuncture or from a separate catheter, other than the catheter used for the infusion, to prevent any contamination of the PK blood samples with lefamulin from the infusion line and catheter.

Plasma samples will be analyzed for concentrations of lefamulin and its metabolite BC-8041 using a validated liquid chromatography-tandem mass spectrometry (LC-MS/MS) method at the bioanalytical laboratory.

The maximum total blood volume collected in the study for safety and PK evaluations is 36 mL per patient.

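### The synopsis and Table 1 disagree on post-dose ECGs, IV time zero is undefined, and on neither reading is an ECG scheduled at the end of the infusion

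*Protocol*

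**What the plan says.** The safety paragraph of the Protocol synopsis reads: "Electrocardiograms will be performed at Screening, pre-dose on Day 1, and at 0.5 and 2 hours post-dose". It does not distinguish the IV from the oral period.

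Table 1 marks an ECG at 0.5 h with footnote g, "IV Treatment Period only (following IV dosing", and an ECG at 2 h with footnote h, "Oral Treatment Period only (following oral dosing". A pre-dose ECG is also scheduled on Day 1 of each period. Section 8.5 gives no times of its own: "A 12-lead ECG will be performed at the time points specified in Table 1".

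Footnote l of Table 1 sets the infusion: "IV dose infused over 1 hour (± 2 minutes". The assessment-window row allows ± 5 minutes at both 0.5 h and 1 h. Section 8.6.1 gives the plasma times for both periods as "Pre-dose; 30 min, and 1, 1.5, 2, 4, 8, 12, and 24 hours post-dose". Nowhere is it stated whether IV post-dose times count from the start or the end of the infusion.

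One decision rests on the post-dose ECG (section 8.5): "If the patient has prolongation of the QTc interval or any arrhythmia during the post-dose ECGs, no further lefamulin should be administered". ECG parameters are a secondary endpoint (section 4.2.2). Section 11.6 summarizes them, with change from baseline, by treatment and scheduled assessment.

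**The concern.** Two things look wrong. First, the synopsis and Table 1 give different schedules, so a site that follows one as written departs from the other. Second, under Table 1 a single scheduled post-dose ECG has to represent the IV dose, and its position relative to the infusion is not fixed.

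For a constant-rate infusion with linear kinetics, plasma concentration is highest when the infusion stops. An ECG well before or after that moment would tend to show less of a QTcF effect that follows concentration. The IV change-from-baseline summary could then be too small. A patient randomized to IV first could also go on to the oral dose 4 to 7 days later without an ECG having been examined at the IV peak.

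The protocol treats QT as a risk: see exclusion criteria 2, 3, 5 and 8 in section 6.2, and Appendix 2, which lists QT-prolonging co-medication for both the injection and the tablets. A SAP cannot recover an ECG that was never recorded.

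**Working it through.** The protocol gives no figure to reproduce here. The check compares the schedules, works out the timing, and then scales the result with an illustrative concentration model.

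**Step 1. The schedules side by side (12 patients, 2 periods).**

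| | IV post-dose ECG | Oral post-dose ECG | Planned total |
|---|---|---|---|
| Synopsis, read literally | 0.5 h and 2 h | 0.5 h and 2 h | 12 × 2 × 2 = 48 |
| Table 1, footnotes g and h | 0.5 h | 2 h | 12 × 2 × 1 = 24 |

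The synopsis line for vital signs (0.5, 2 and 24 h) agrees with its Table 1 row, so the ECG mismatch is unlikely to come from a badly extracted table.

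**Step 2. Where the 0.5 h IV ECG falls.** Inputs: ECG at 30 ± 5 minutes (Table 1) and infusion of 60 ± 2 minutes (footnote l).

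- *Time zero at the start of infusion.* Nominal 30/60 = 50% of the infusion, or 75 of 150 mg. Extremes: 25/62 = 40.3% and 35/58 = 60.3%. The ECG precedes the peak.
- *Time zero at the end of infusion.* The ECG falls 25 to 35 minutes after the peak.

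**Step 3. Which reading is likelier.** With time zero at the start, the 1 h plasma sample coincides with the end of infusion and can capture Cmax, a listed parameter in section 4.2.1. With time zero at the end, the first post-dose plasma sample on the same clock would come 30 minutes after the peak. This favors the start. The wording of footnote g, which speaks of ECGs following IV dosing, leans the other way. The section 8.6.1 advice to sample from a catheter "other than the catheter used for the infusion, to prevent any contamination of the PK blood samples" does not settle it, because residue in a line can contaminate samples drawn during or after an infusion.

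**Step 4. Concentration at the ECG relative to the end of infusion.** The protocol gives no half-life, so those below are assumptions. For one compartment with k = ln 2 / half-life and a 1-hour infusion:

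- time zero at start: C(0.5)/C(1) = (1 − e^(−0.5k)) / (1 − e^(−k))
- time zero at end: C(1.5)/C(1) = e^(−0.5k)

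| Assumed half-life | Zero at start | Zero at end |
|---|---|---|
| 12 h | 0.507 | 0.972 |
| 8 h | 0.511 | 0.958 |
| 2 h | 0.543 | 0.841 |
| 1 h | 0.586 | 0.707 |
| 0.5 h | 0.667 | 0.500 |
| 0.25 h | 0.800 | 0.250 |

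At 10 h the start-reading ratio is 0.509. Two-compartment runs (fast half-life 0.15 to 0.5 h, slow half-life 6 to 10 h, fast fraction 0.5 to 0.9) gave 57% to 78% of peak with zero at the start and 38% to 81% with zero at the end.

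**Step 5. Would the synopsis 2 h ECG repair this?** With time zero at the start it falls 1 h after the end of infusion, where C(2)/C(1) = e^(−k): 0.933 at a 10 h half-life, 0.500 at 1 h and 0.250 at 0.5 h. It is at best a partial substitute.

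**The case against.** The strongest reply is that a reader might infer that the IV ECG is definitely mid-infusion. The protocol does not say so. Footnote g can be read as placing the ECG after the infusion, and with a long half-life that position loses little (97% of peak at 12 h). This stands, and the mid-infusion placement is therefore conditional.

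Nor is it shown that the 0.5 h column cannot serve both ECG and plasma. Footnote g attaches to the ECG cell only, so the ECG could be anchored to the end of infusion while plasma runs from the start. The protocol leaves this unstated.

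The schedule conflict has a benign explanation: the synopsis may list the study's ECG times while Table 1 assigns them to routes. Section 8.5 tells sites to use Table 1. The 48-against-24 count applies only to a literal reading of the synopsis.

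The safety exposure is limited. Each route is a single dose at the level recommended for pneumonia, patients at QT risk are excluded, and the Investigator or a designee must review a pre-dose ECG before the second dose. Section 8.5 permits extra ECGs, and individual listings would show them. All of this stands, but it does not close the gap. A pre-dose ECG 4 to 7 days later is unlikely to show a transient peak effect, and a symptom-free patient gives no prompt for an extra ECG at the peak.

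The absence of a time point shared with the oral period is not a fault. Section 11.6 plans descriptive summaries by treatment, and route-specific timing is a legitimate choice.

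**Conclusion.** The point holds in a limited form. The synopsis and Table 1 differ on post-dose ECGs, IV time zero is undefined, and on either reading no scheduled ECG falls at the end of the infusion. If time zero is the start, the only scheduled post-dose IV ECG comes at 40% to 60% of the infusion and, under the one-compartment assumptions, at about 51% to 80% of peak concentration. If it is the end, the ECG comes about 30 minutes after the peak, at about 25% to 97%.

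The consequence is possible, not demonstrated: a QTcF effect could be understated and the stopping rule could miss it, provided the effect tracks plasma concentration. No size in milliseconds follows, because the protocol gives neither a half-life nor a concentration–QTcF relation. A reader might also infer that the IV period has only one ECG, but it has a scheduled pre-dose ECG as well.

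This is worth correcting because the change is cheap and concerns a secondary safety endpoint and a stopping rule. It does not touch the primary PK objective, provided plasma times run from the start of infusion.

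**What to change.** 1. State that time zero in the IV period is the start of infusion, for ECG, vital signs and plasma alike.
2. In Table 1, move the IV post-dose ECG from the 0.5 h column to the existing 1 h column, and word footnote g so that it is recorded just after the infusion stops. The ± 5 minute window alone is not enough: 55 to 65 minutes against an infusion of 58 to 62 minutes could still put the ECG before the end.
3. Rewrite the synopsis ECG line to give the Table 1 times by route.

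The cost is one added sentence and edits to one Table 1 row, one footnote and one synopsis line. The number of IV post-dose ECGs stays at 12 × 1 = 12, and plasma is already drawn at 1 h. A further 2 h ECG in the IV period would add 12 ECGs at a time when vital signs and plasma are already taken. It is optional and not needed to resolve this point.

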#### 3.3.2. Dose Rationale

For treatment of adults with CABP, the recommended dosage regimen of lefamulin is as follows:

- 150 mg every 12 hours (q12h) by IV infusion over 60 minutes for 5 to 7 days, or
- 150 mg q12h by IV infusion over 60 minutes then switch to 600 mg orally q12h (at the discretion of the physician) for 5 to 7 days total, or
- 600 mg orally q12h for 5 days.

Nabriva Therapeutics Lefamulin

In this study, single doses of IV and oral lefamulin will be studied in CF patients; PK data from this study will be sufficient to compare exposure in these patients to the known exposure in non-CF patients. The single doses to be evaluated in adults will be those recommended for treatment of CABP, ie, 150 mg IV or 600 mg orally.

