## 4.2. Endpoints

#### 4.2.1. Primary Endpoint

Plasma PK of lefamulin and its main metabolite, BC-8041, following 150-mg IV infusion and 600-mg IR tablet in patients with CF.

Appropriate non-compartmental techniques will be used to obtain estimates, including but not limited to, the following PK parameters in plasma for lefamulin and its metabolite BC-8041 when possible and appropriate:

- Cmax: maximum observed plasma concentration
- tmax: time to reach maximum plasma concentration of lefamulin following drug administration
- AUC0-12h: area under the drug concentration curve from time zero (0 hour [h]) to 12 h
- AUC0-24h: area under the drug concentration curve from time zero (0 h) to 24 h
- AUC0-last: area under the drug concentration curve from time zero (0 h) to 24 h
- AUC $_{\infty}$  area under the drug concentration curve from time zero (0 h) to infinity
- $t_{1/2}$ : apparent elimination half-life calculated as  $ln(2)/k_e$
- CL: clearance (IV dose only)
- CL/F: total body clearance (oral dose only)
- Tlag (oral dose only): the finite time taken for a drug to appear in systemic circulation following extravascular administration
- AUC%extrap: percentage of AUC due to extrapolation for infinity

02 November 2021 21 Confidential

- lambda-z: Individual estimate of the terminal elimination rate constant, calculated using log-linear regression of the terminal portions of the plasma concentration-versus-time curves
- Vd (IV dose only): volume of distribution
- Vd/F (oral dose only): volume of distribution corrected for bioavailability
- Vss (IV dose only): volume of distribution at steady state
- MRT: mean residence time
- F: oral bioavailability

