## 7.3. Treatment Compliance

Study personnel will observe administration of each oral dose of lefamulin to each patient while at the investigative site. A mouth and hand check will be performed to ensure patients took the full dose provided. The study personnel will administer the IV infusion of lefamulin at the investigative site.

The dose and date/time of the administration of the study drug will be recorded in the site source documents and in the appropriate sections of the electronic case report form (eCRF).

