#### 11. STATISTICAL ANALYSIS

### 11.1. Sample Size Determination

Target enrollment for this study will be 12 patients.

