# 11.4. Pharmacokinetic Analysis

Presentation of PK data will be descriptive in nature and will be presented by treatment.

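### The single plasma sample near the end of the IV infusion may be drawn up to 7 minutes either side of the actual stop, so observed IV Cmax can only miss the peak low, modestly on average

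*Protocol*

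**What the plan says.** Footnote l of Table 1 in the protocol gives the infusion tolerance: "IV Treatment Period: IV dose infused over 1 hour (± 2 minutes". The row of Table 1 labelled "Assessment window" gives ± 5 min for the 0.5 h and 1 h columns and ± 10 min for 1.5 h. One row serves both the IV and the oral period.

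Section 8.6.1 lists the plasma samples: "Pre-dose; 30 min, and 1, 1.5, 2, 4, 8, 12, and 24 hours post-dose". It does not say whether post-dose time after an infusion is counted from its start or its end. Nor does any section tie a sample to the moment the infusion stops. Section 8.6.1 recommends venipuncture or a separate catheter and leaves collection details to a Laboratory Manual that is not part of the protocol.

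Section 4.2.1 lists Cmax among the primary-endpoint parameters and defines it as "maximum observed plasma concentration". Section 3.3.2 says that "PK data from this study will be sufficient to compare exposure in these patients to the known exposure in non-CF patients". Section 7.3 says that "The dose and date/time of the administration of the study drug will be recorded", without naming an infusion stop time. Section 11.1 sets the size ("Target enrollment for this study will be 12 patients"), and section 11.4 the analysis: "Presentation of PK data will be descriptive in nature and will be presented by treatment".

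**The concern.** During a constant-rate infusion the concentration rises until the infusion stops and then falls, steeply if distribution is fast. A sample before the stop has not reached the peak, and a sample after it has passed the peak. Both errors point the same way, so they do not cancel over patients as ordinary timing noise would. Cmax is taken as observed, so the shortfall enters the parameter directly, and no analysis rule can restore a peak that was not sampled.

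At stake are IV Cmax and tmax, and whatever part of the comparison with non-CF patients rests on them. Section 3.3.1 gives altered distribution and elimination in CF as part of the rationale. The speed of distribution also governs how much a late sample loses, so a timing artefact and a disease effect on Cmax could be hard to tell apart.

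**Working it through.** The plan states no figure for the precision or bias of Cmax, so there is none to reproduce. The schedule arithmetic comes from the protocol. The sizes need half-lives that the protocol does not give; those below are assumptions.

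**Schedule, counted from the start of infusion**

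- Infusion end: 60 ± 2 = 58 to 62 min (footnote l).
- 1 h sample: 60 ± 5 = 55 to 65 min (Table 1).
- Neighbouring samples: 30 ± 5 = 25 to 35 min, and 90 ± 10 = 80 to 100 min.
- Earliest draw relative to the stop: 55 − 62 = −7 min. Latest: 65 − 58 = +7 min.

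**Model.** For a unit dose infused over T minutes, with bolus response Σ A·exp(−λt) and λ = ln 2 / half-life:

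- t ≤ T: C(t) = Σ [A/(λT)]·(1 − exp(−λt))
- t > T: C(t) = Σ [A/(λT)]·(1 − exp(−λT))·exp(−λ(t − T))

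**One case by hand.** Assume a 10 min distribution half-life carrying 90% of the bolus response, an 8 h terminal half-life, and T = 60. Then λ = 0.06931 and 0.001444 per min, and A/λ = 12.984 and 69.249. Dropping the common factor 1/T:

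- C(60) = 12.781 + 5.747 = 18.529 (terms rounded)
- C(65) = 12.781 × 0.7071 + 5.747 × 0.9928 = 9.038 + 5.706 = 14.744; ratio 0.796, so 20.4% low
- C(55) = 12.697 + 5.287 = 17.985 (terms rounded); ratio 0.971, so 2.9% low

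**Range of models.** Infusion end and all sample times are uniform over their permitted windows, with 100,000 draws per model. Observed Cmax is the largest of the 0.5, 1 and 1.5 h samples, compared with the concentration at the actual stop. Entries are % below the true peak (SD in percentage points). The two extreme columns hold the neighbouring samples at 30 and 90 min. The last column draws the sample within the 2 min before the actual stop.

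| Assumed model | Mean | SD | 5th percentile | Draw 55, stop 62 | Draw 65, stop 58 | Mean, tied to stop |
|---|---|---|---|---|---|---|
| 1-compartment, 8 h | 1.7 | 1.7 | 4.8 | 4.0 | 1.0 | 1.6 |
| 1-compartment, 2 h | 2.6 | 2.1 | 7.0 | 9.6 | 4.0 | 1.4 |
| 2-compartment, 30 min, 70% fast | 3.2 | 2.0 | 6.8 | 7.8 | 9.0 | 1.1 |
| 2-compartment, 15 min, 80% fast | 4.5 | 3.8 | 12.4 | 5.9 | 16.8 | 0.8 |
| 2-compartment, 10 min, 90% fast | 6.3 | 6.6 | 19.4 | 4.0 | 21.9 | 0.6 |
| 2-compartment, 5 min, 90% fast | 8.3 | 8.2 | 23.4 | 5.2 | 22.6 | 0.8 |

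The two-compartment models use an 8 h terminal half-life. No draw exceeded the true peak. Losses of 20% or more appear only in the last two models, and there the early extreme costs just 4 to 5%, so they come from late draws. With the sample tied to the stop, the worst single value over all six models is 3.3% low.

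**Effect on the reported CV.** The documents give no CV for Cmax. Assume 20, 30 or 40% and add the SD of 1.7 to 8.2 points in quadrature:

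- 20%: √(20² + 1.7²) = 20.1 to √(20² + 8.2²) = 21.6
- 30%: 30.05 to 31.1
- 40%: 40.0 to 40.8

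**Sampling error for scale.** With 12 patients and a 30% CV, the standard error of the mean is 30/√12 = 8.7%; with 20% it is 20/√12 = 5.8%.

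**The case against.** The best reply is that little hangs on this. The nominal 1 h sample already coincides with the nominal end of infusion. PK presentation is descriptive, there is no acceptance limit, and Cmax is one of 17 parameters listed in section 4.2.1. Section 3.3.2 speaks of exposure without naming Cmax. If real times cluster around nominal, the loss shrinks: with distribution half-lives of 10 to 45 min, 60 to 90% in the fast phase and a 10 h terminal half-life, the mean shortfall is 1.9 to 4.4% with triangular timing, against about 2.8 to 6.4% with uniform timing. At a 30% CV the standard error with 12 patients exceeds every mean shortfall in the table. The Laboratory Manual may already set a tighter draw. All of this stands and holds the severity down. It does not change the direction of the error, and if the manual is tighter, Table 1 should agree with it.

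The point also depends on post-dose time running from the start of infusion. If it ran from the end, the 1 h sample would lie an hour past the peak and its ± 5 min would be irrelevant. The first sample would come 30 min after the stop, 4 to 62% below the peak under the same models. That would be a different and larger problem, and it is one more reason to state time zero.

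A reader might go further and infer that IV Cmax will be about a quarter too low. A figure near 27% does arise for the 1 h concentration, but only with a 58 min infusion, a 65 min draw, a 10 min distribution half-life and 90% of the response in the fast phase. Draws more than 6 min after the stop make up about 1% of uniform timings. In that corner the 0.5 h sample is the higher one, so observed Cmax itself is about 22% low. The documents support no such figure as typical.

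**Conclusion.** The point holds as a minor one. Counted from the start of infusion, the protocol lets its only near-peak IV sample fall up to 7 min either side of the stop, and observed IV Cmax is then at or below the true peak, leaving aside assay error and line contamination. The likely mean shortfall is about 2 to 8%, on half-lives that are assumed rather than documented.

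Two further inferences are not supported. One is that the between-patient CV is materially inflated: the increase is at most 1.6 points in the cases computed. The other is that the comparison with non-CF exposure is invalid. It is distorted only to the extent that the reference studies sampled the end of infusion differently, and the protocol does not describe their sampling. The finding concerns IV Cmax and tmax; AUC, and the clearance and bioavailability derived from it, are little affected if actual times are used.

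**What to change.** For the IV period only, in Table 1 and section 8.6.1:

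- State that time zero is the start of infusion.
- Replace the 1 h ± 5 min sample by one tied to the actual end of infusion, for example within the last 2 minutes before the pump is stopped.
- Record the actual infusion stop time and the actual draw time in the eCRF. Section 7.3 already records the dosing date and time, so the stop time is the explicit addition on the dosing side.

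Leave the oral window unchanged. The separate draw site in section 8.6.1 needs no change, and the Laboratory Manual should match the new wording.

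The cost is a footnote and one or two eCRF fields, with no extra sample, blood or visit. A tighter draw window at approximately 6 centers will probably produce some timing deviations. The gain depends on the drug's distribution: under the assumed models the mean shortfall falls to 0.6 to 1.6%. That is almost no gain on average in the slowest model (1.7 to 1.6%) and a clear one in the fastest (8.3 to 0.8%).
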